6. STATISTICAL CONSIDERATIONS

6.1. General

For continuous variables, summary tables will provide the number of observations [n], mean, standard deviation, median, minimum, and maximum. For categorical variables, summary tables will provide the number of observations [n] and frequency of each category (including missing data). Tabulations will be presented by treatment and overall, when appropriate. Modelling and testing will be described for each endpoint.

Study day for specific measurement is calculated as (date – date of baseline visit). Run-in period will include study days -28 until -1. Day 0 is the baseline day and days >=1 are treatment period days.

Measurements taken at Early Termination visit/withdrawal will be presented in listings but will not be included in summaries and analyses.

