#### Baseline Virtual Visit (Day 1)

|                                | 
 
After completing the 28-day run-in period, the participant will be contacted for a Baseline Visit to review and confirm eligibility. Participants will be considered eligible for study entry based on all of the following criteria:
 
Continuing to meet all other inclusion and no exclusion criteria, based on investigator assessment.
 
Understanding of and adherence to the onboarding requirements and Study App (at 80% or greater adherence).
 
 |
|--------------------------------|--|
|                                | 
 
Reporting within the Study App between 4-14 migraine days (inclusive) during the 28-day run-in period.
 
Agreeing to complete the 12-week study intervention in good faith at the time of baseline virtual visit.
 
   |
|                                | Eligible participants will then be randomly assigned in a 1:1 ratio (CT-132: Digital Control) and the assigned full therapeutic app will be activated. Assessments and activities during this period will be performed remotely by telemedicine technology visits according to the SoA (Section 1.2).  |
|                                | Double-Blind Intervention Period (12 Weeks)  |
|                                | During the 12-week intervention period, the Study App will deliver either CT-132 or the Digital Control. Participants may use their prescribed medication to treat episodic migraine (including changes in medication or dosage) as needed while continuing to use the Study App on their regular schedule. Assessments and activities during this period will be performed remotely according to the Schedule of Activities and Assessments (Section 1.2).                                |
|                                | Follow-Up Period (Up to 1 week)  |
|                                | Within one week of completion of the 12-week intervention period or withdrawal from the study, participants will complete the follow-up activities according to the Schedule of Activities and Assessments (Section 1.2).  |
| Planned Number of Participants | Approximately 558 participants will be randomized in this study.   |
| Study Centers                  | This will be a fully virtual study. Participants living in the United States will be enrolled and followed remotely through telemedicine visits.   |

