| Study Visit Number a | n/a                    | 1              | 2                        | 3                  | 4                  | 5                  | 6              |
| Study App Deactivation          |                        |                |                          |                    |                    | X g     |                |
| Concomitant Medications         | X                      | X              | X                        | X                  | X                  | X                  | X              |
| Adverse Events                  | X                      | X              | X                        | X                  | X                  | X                  | X              |

[figure not shown]
Abbreviations: DOSE-Nonadherence measure = Domains of Subjective Extent Nonadherence measure; ET = Early Termination; ID-CM = Identify Chronic Migraine; MIDAS = Migraine Disability Assessment Scale; MSQ = Migraine-Specific Quality-of-Life Questionnaire; PGI-C = Patient Global Impression of Change scale;

- a. All study visits are virtual and conducted via telemedicine.
- b. Screening Visit may occur up to fourteen (14) days before the run-in period.
- c. Follow-Up activities, to include revealing the trial hypothesis, to occur within one week of the final intervention period visit. This is at least one day after the Week 12 visit (between Day 86 and Day 92) or at least one day, but no more than seven days, after an Early Termination visit.
- d. Only the eDiary component of the Study App is used by the participant to complete run-in period activities. The run-in period consists of 28 days of data. However, per Study App design, participants may enter Day 28 data until Day 30. The Baseline Visit window will begin after Day 30.
- e. The full Study App is used every day by the participant during the indicated period.
- f. Adherence checks occur at baseline to confirm eligibility and as needed throughout the intervention period when a participant does not perform Study App Activities for 3 calendar days per Section 6.4.
- g. After completion of the intervention period (Day 84), the Study App will become inert. After Day 84, or upon study withdrawal, participants will not have continued access to the content provided by the Study App.

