#### 4.1.2. **Run-In Period (Day -28 to Day -1)**

After completing the study onboarding activities, eligible participants will be contacted to schedule a remote video call to verify their identity and their migraine medication prescriptions. Once reviewed and verified, participants will be introduced to the Study App by downloading and installing the application onto their personal iPhone or Android smartphone. Only the eDiary component of the Study App will be activated. The eDiary contains items from the Migraine Disability Index (MIDI).

Participants will then enter a 28-day run-in period during which they will enter daily headache information within the Study App to establish their baseline MMD and determine their adherence to and interest in the Study App. Adherence to the onboarding requirements will be assessed by the investigator prior to randomization at the baseline visit. Activities and assessments during this period will be performed remotely between the study personnel and the participant.

The run-in period consists of 28 days of data. However, participants may enter data at Day 28 through Day 30. The Baseline Visit window will begin after Day 30.

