#### 4.1.3. Baseline Virtual Visit (Day 1)

After completing the 28-day run-in period, eligible participants will have 3 days to complete baseline activities. Participants will attend a Baseline Visit via a telephone call to review and confirm eligibility. Participants will be considered eligible for study entry based on all of the following criteria:

- Continuing to meet all other inclusion and no exclusion criteria, based on investigator assessment.
- Understanding of and adherence to the onboarding requirements and the Study App
- Reporting within the Study App between 4-14 migraine days (inclusive) during the 28-day run-in period.
- Agreeing to complete the 12-week study intervention in good faith at the time of baseline virtual visit.

Eligible participants will then be randomly assigned in a 1:1 ratio (CT-132:Digital Control). The Study App downloaded during the run-in period will be utilized to deliver the full therapeutic app. Participants will continue to utilize the eDiary component in the Study App throughout the study.

The process for activating and accessing the full therapeutic application during the Baseline Visit will be the same for CT-132 digital intervention and the Digital Control. The randomization process electronically unlocks one of two experiences in the Study App: the CT-132 investigational therapy or the Digital Control. Study staff will complete the randomization process by giving the participant a code to proceed in the Study App. This code serves as a gatekeeper to confirm that the randomization process has been completed correctly and that the participant may continue in the study. This randomization process is designed in a way to minimize unblinding risk for the participant and the study staff. Participants are considered enrolled upon randomization.

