6.2. Specification of Baseline Values

A participant's baseline MMDs/MHDs will be the total number of headache/migraine days recorded during the 28-day run-in period. Baseline MMDs is a subset of baseline MHDs.

For endpoints not mentioned above, a baseline value is the latest value measured during the baseline visit or prior to baseline visit.

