6.3. Handling of Missing Data

Participants should complete the eDiary on a daily basis during the 28 days of the run-in period and the 12 weeks of treatment. In the eDiary, the participants report whether they experienced a headache during that day including the start and end time, symptoms, and usage of acute medications. The eDiary allows for retrospective reporting of headaches up to 48 hours.

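### Read with the protocol's Day 30 rule, the date-based run-in window in SAP 6.1 misses at least 2 of the 28 baseline diary days and should be anchored to the diary

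*SAP*

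**What the plan says.** SAP 6.1 sets study day as the date minus the date of the baseline visit, then: "Run-in period will include study days -28 until -1. Day 0 is the baseline day and days >=1 are treatment period days". It is the only printed SAP rule that attaches dates to the run-in.

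SAP 6.2 says that baseline MMDs and monthly headache days (MHDs) "will be the total number of headache/migraine days recorded during the 28-day run-in period", and SAP 8.1.1 repeats this for the primary endpoint. SAP 6.3 describes when diaries are due: "Participants should complete the eDiary on a daily basis during the 28 days of the run-in period and the 12 weeks of treatment". SAP Section 8 refers the MMD derivation to Appendix A, Section 7, which is not in the public text.

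Protocol 4.1.2 says: "The run-in period consists of 28 days of data". Footnote d of the Schedule of Activities (Protocol 1.2) adds that "participants may enter Day 28 data until Day 30. The Baseline Visit window will begin after Day 30", and Protocol 4.1.2 repeats the Day 30 rule. On how late the visit may be, the schedule gives Day 1 + 5 days, while Protocol 4.1.3 says "eligible participants will have 3 days to complete baseline activities". The same section makes eligibility depend on "Reporting within the Study App between 4-14 migraine days (inclusive) during the 28-day run-in period".

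The baseline day is Day 0 in SAP 6.1 and Day 1 in the protocol.

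**The concern.** A window counted back from the visit coincides with the 28-day diary only if the visit falls on the day after the diary ends. The protocol rules that day out, so the literal SAP window is late for every participant seen within the visit window.

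Baseline MMD is subtracted in the primary endpoint and is a covariate in the primary ANCOVA (SAP 8.1.3). It is also the denominator of the 50% responder endpoint (SAP 8.5.1) and sets high or low frequency class (SAP 8.8.1). Eligibility uses the actual 28-day run-in. If the analysed baseline covers other days, SAP 8.8.1's statement that no participant has very low frequency migraine (fewer than 4 MMDs) at baseline is not guaranteed.

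SAP Section 1 gives the SAP precedence where the two documents disagree, so the protocol wording does not by itself settle which days count.

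**Working it through.** **The SAP's own figure.** Study days -28 to -1 are 28 days, so the stated length reproduces. Within the SAP alone there is no clash.

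**The shift.** Number the run-in diary days 1-28 and put the baseline visit on run-in Day V. Study day = run-in day - V, so the SAP window is run-in Days V-28 to V-1 and starts V-29 days late. A shift of zero needs V = 29. A visit after Day 30 means V is at least 31, so the minimum shift is 31 - 29 = 2 days.

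| Visit (run-in day) | Window | Shift | Intended days kept |
|---|---|---|---|
| 29 (excluded by protocol) | 1-28 | 0 | 28 |
| 31 (earliest) | 3-30 | 2 | 26 |
| 33 | 5-32 | 4 | 24 |
| 34 | 6-33 | 5 | 23 |
| 36 | 8-35 | 7 | 21 |

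At the minimum, 2/28 = 7.1% of the intended days are lost.

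**The maximum is unclear.** The 3-day allowance ends on Day 31 if counted from Day 29, or on Day 33 if counted from Day 31. The + 5 days ends on Day 34 if nominal Day 1 is run-in Day 29, or on Day 36 if counted from Day 31. The protocol does not reconcile them.

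**Illustration at the cut-offs.** The assumptions are a 2-day shift, migraine days exchangeable over the run-in, and diary entries continuing in the two gap days at rate r. With B migraine days in the run-in, days lost L ~ Hypergeometric (2 drawn from 28, B migraine days), days gained G ~ Binomial(2, r), and the analysed baseline is B - L + G. First take r = B/28.

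- B = 4, r = 1/7: P(L=1) = 96/378 = 0.254; P(L=2) = 6/378 = 0.016; P(G=0) = 0.735; P(G≤1) = 0.980. P(below 4) = 0.254 × 0.735 + 0.016 × 0.980 = 0.202.
- B = 8, r = 2/7: P(L=1) = 160/378 = 0.423; P(L=2) = 28/378 = 0.074; P(G=0) = 0.510; P(G≤1) = 0.918. P(below 8) = 0.423 × 0.510 + 0.074 × 0.918 = 0.284.
- One day above each cut-off the probabilities are small: 1.8% for B = 5 and 4.4% for B = 9. From B = 6 and B = 10 upward they are zero.
- At the upper limit, 31.0% of those with exactly 14 would exceed 14.

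With gap-day entries at half the run-in rate (r = B/56), the figures for exactly 4, 8 and 14 become 23.5%, 38.4% and 13.8%.

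If the gap days hold no entries, a complete run-in diary fills 26 of the 28 window days. An unimputed count would then be low by B × 2/28 on average: 0.29 days at B = 4 and 1.0 at B = 14.

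**Effect on the primary comparison.** If change = Week 12 - B is modelled as a + τ·arm + β·B + other terms, then Week 12 = a + τ·arm + (β + 1)·B + other terms. The treatment coefficient τ is the same, so baseline affects the comparison only through covariate adjustment. I simulated a 2-day shift with independent days, continued entries and daily migraine rates drawn from Beta(4,10), Beta(2,5) or Beta(8,20), all assumed. The shifted and intended baselines correlated at 0.94-0.96, mean baseline moved by less than 0.01 day, and the ratio of adjusted standard errors was about 1.00. Longer shifts and empty gap days were not simulated.

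**The two clocks.** SAP Day d is protocol Day d + 1. The SAP's Days 1-28 (8.5.2) and 29-56 (8.5.3) are therefore protocol Days 2-29 and 30-57, and the activation day falls in neither.

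**The case against.** The strongest reply is that SAP 6.1 is a general convention and not the operative derivation. Appendix A, Section 7 and most of SAP 6.3 cannot be seen and may already count diary days. The protocol also labels the run-in Days -28 to -1, so SAP 6.1 may simply repeat a nominal label. The SAP says it should be read with the protocol and is meant to agree with it. This stands to the extent that nobody can say the baseline as actually derived is wrong. It does not remove the conflict in the printed rule, because SAP 6.1 ties day numbers to the actual visit date, which a nominal label does not.

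A reader might infer that the primary treatment difference is biased because baseline is subtracted in the endpoint. The documents do not support that. The window precedes randomisation, applies alike to both arms, and baseline is also a covariate, so the primary comparison is essentially unaffected.

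The loss of 7.1% applies only to unimputed counts. SAP 8.1.1 imputes missing diary days for the primary analysis, so that loss would reach only observed-data outputs, such as the baseline table (SAP 7.2) and the no-imputation analysis (SAP 8.3.2). Imputation is also a separate reason why the analysed baseline may differ from the eligibility count. If the synopsis's 80% adherence means diary days, 0.8 × 28 = 22.4, so at least 23 days are needed and up to 5 may be missing. The SAP 6.1 shift comes on top of this and affects complete diaries too.

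Leaving a partial activation day out of the treatment windows can be a defensible convention.

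**Conclusion.** The conflict holds on the printed text. With visits only after run-in Day 30, the literal SAP 6.1 window loses at least 2 of the 28 intended days and takes in at least 2 days with no scheduled diary. That minimum needs no assumption beyond the two documents; the maximum cannot be fixed from them.

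The impact is modest. It falls on baseline accuracy, within-arm change, the 50% responder endpoint, and high/low frequency class. The probabilities of about 20% (exactly 4 MMDs) and 28% (exactly 8) apply only to participants at those cut-offs and rest on the exchangeability and gap-day assumptions above. A reader might scale them to the 558 randomised, but the documents give no baseline distribution, so trial-wide counts cannot be derived.

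A reader might also extend the SAP's day numbers to Days 57-84 for Weeks 9-12, which would be protocol Days 58-85, and infer that the window runs past app deactivation after Day 84. That is not established. The SAP does not print the Weeks 9-12 days, and the protocol places the Week 12 assessments at Day 84 in Section 4.4 but at Day 85 in the schedule, so it is unclear which clock its Day 84 uses. What holds is that the baseline day has two numbers and needs one.

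**What to change.** - In SAP 6.1, define the run-in for MMDs and MHDs as run-in diary Days 1-28, counted from the start of the run-in eDiary and independent of the baseline visit date. The shift is then 0 and all 28 intended days are kept, whatever the visit date.
- Confirm that Appendix A, Section 7 and SAP 6.3 use the same days. If they already do, align 6.1 with them.
- Number the baseline day on one clock across the protocol and SAP, and state the Weeks 9-12 days on that clock in SAP 8.1.1.
- Reconcile the two baseline visit allowances in the protocol (+ 5 days and 3 days).

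The cost is wording and derivation programming before database lock. Data collection, sample size and trial conduct do not change.

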## 7. DISCONTINUATION OF STUDY INTERVENTION AND PARTICIPANT DISCONTINUATION/WITHDRAWAL

#### 7.1. Discontinuation of Study Intervention

In rare instances, it may be necessary for a participant to permanently discontinue study intervention. If study intervention is permanently discontinued, the participant will complete early termination assessments as per the SoA (Section 1.2).

Events that could result in permanent discontinuation of study intervention include:

- Nonadherence
- Use of prohibited concomitant medications
- Use of prohibited recreational medications
- Investigator's discretion

The Study App on the discontinued participant's smartphone device will be disabled as described in Section 6.2.

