### 7.2. Participant Discontinuation/Withdrawal from the Study

Study staff should make every effort to encourage participants to remain in the study and to continue to use the Study App. A participant may withdraw from the study at any time at their own request or may be withdrawn at any time at the discretion of the investigator for safety, behavioral, or compliance reasons. This is expected to be uncommon.

A participant cannot withdraw consent for use of data already collected as part of the study. If the participant withdraws consent for disclosure of future information, the sponsor may retain and continue to use any data collected before such a withdrawal of consent.

Participants who prematurely discontinue study participation must complete the early termination procedures as described in the SoA (Section 1.2). Participants who discontinue use of the Study App prematurely should ideally be observed until the end of the study as if they were still using the Study App. The Study App on the discontinued participant's smartphone device will be disabled as described in Section 6.2. For all participants, the reason for discontinuation (e.g., AEs) must be recorded in the eCRF. These data will be included in the study database and reported.

Participants who are not actively using the Study App may be less motivated to adhere to the study visit schedule. Investigators and study staff should work to detect early signs of waning interest and encourage continued participation.

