#### 8.4.1. Time Period and Frequency for Collecting AE and SAE Information

All AEs and SAEs will be collected from the signing of the informed consent form (ICF) until the follow-up visit at the time points specified in the SoA (Section 1.2).

AEs will be divided into non-treatment-emergent AEs (non-TEAEs) and treatment-emergent AEs (TEAE). Non-TEAEs are those AEs that occurred prior to the first study treatment and TEAEs are those AEs with onset date/time at or after the first study treatment.

All SAEs will be recorded and reported to the sponsor or designee immediately and under no circumstance should this exceed 24 hours, as indicated in Appendix 3. The investigator will submit any updated SAE data to the sponsor within 24 hours of it being available.

Investigators are not obligated to actively seek information on AEs or SAEs after conclusion of the study participation. However, if the investigator learns of any SAE, including a death, at any time after a participant has been discharged from the study, and he/she considers the event to be reasonably related to the study intervention or study participation, the investigator must promptly notify the sponsor.

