2.2. Primary Estimand

The primary estimand will be the effect of the digital therapeutic (CT-132) on number of MMDs regardless of use of prohibited medications, adherence to treatment or early termination for any reason.

This estimand considers the following intercurrent events:

- Use of prohibited medications
- Lack of adherence
- Early discontinuation due to any reason

Since participants may use their prescribed medication to treat episodic migraine (including changes in medication or dosage) as needed while continuing to use the Study App, and since the study population is defined as participants diagnosed with migraine and taking first- and second-line preventive medications, the use of these medications is not considered an intercurrent event.

Attributes of the primary estimand:

- The **treatment condition** of interest is CT-132 compared to a digital control, both alongside prescribed medications, to treat episodic migraine
- The **population** is late adolescents and adults with episodic migraine who fulfill all of the inclusion criteria and none of the exclusion criteria for the study
- The **endpoint** to be considered is the change from baseline (28-day run-in period) in MMDs to week 12 (previous 28 days, Weeks 9-12)
- The **population-level summary** is the least squares mean (LSM) difference between CT-132 and the digital control

Strategies for Addressing Intercurrent Events in Primary Estimand

- Use of prohibited medications: In case of use of prohibited medications, participants will be discontinued from the study and the Study App will be disabled for them. Data accumulated until the Study App is disabled will be included in the analysis. This approach complies with the treatment policy strategy.
- Lack of adherence: The treatment effect of CT-132 will be estimated regardless of lack of adherence to lessons and activity. This approach complies with the treatment policy strategy.

• Early discontinuation due to any reason: The treatment effect of interest is regardless of early discontinuation of treatment which complies with the treatment policy strategy. For that reason, data that does not exist after early discontinuation will be considered as missing data, and will be imputed as described in Section 6.3.

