8.5.5. Change in the number of headaches with at least moderate severity from baseline (28-day run-in period) to Week 12 (previous 28 days, Week 9 through Week 12)

This endpoint will be performed on the mITT analysis set, in addition to the ITT analysis set.

Each recorded headache's severity will be scored in the following manner:

- None = 0
- Mild = 1
- Moderate = 2
- Severe = 3

Headaches that started at one period and ended in the following period will be assigned to the period in which the headache started.

The change from run-in will be calculated as (Weeks 9-12 number of headaches with at least moderate severity – run-in number of headaches with at least moderate severity).

An ANCOVA model will be used to analyze this endpoint. The dependent variable is the change in number of headaches with at least moderate severity from run-in period to Week 9-12 for each participant.

The model will adjust for the following covariates: treatment arm and number of headaches with at least moderate severity at run-in period

This analysis will use observed data only.

8.5.6. Change from baseline in the Migraine-Specific Quality-of-Life Questionnaire v2.1 (MSQ) total score at Week 12

The MSQ is a 14-item questionnaire that is completed at baseline, Week 4, Week 8, and Week 12. Each item consists of 6 possible responses, scored 1 to 6. Higher scores represent more severe migraines.

For the purpose of calculating the MSQ total score, the responses to the 14 items will be reverescoded (scores 1,2,3,4,5,6 will be converted to 6,5,4,3,2,1 respectively)

For each visit, the MSQ score (after reverse-coding) will be calculated as:

Total score = ([sum of the 14 reversed item scores - 14] / 70) * 100

In case of missing items, the MSQ score for the visit will be considered missing.

An ANCOVA model will be used to analyze this endpoint. The dependent variable is the change from baseline in MSQ to week 12 for each participant.

The model will adjust for the following covariates: treatment arm and baseline MSQ.

This analysis will use observed data only.

8.5.7. Change from baseline in the Migraine-Specific Quality-of-Life Questionnaire v2.1 (MSQ) total score at Week 8

This endpoint will be analyzed in the same manner as described in Section 8.5.6, using the Week 8 assessment.

8.5.8. Change from baseline in the Migraine-Specific Quality-of-Life Questionnaire v2.1 (MSQ) total score at Week 4

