9. SAFETY ANALYSIS

All safety analyses will be conducted on the safety analysis set and will be descriptive.

AE will be recorded from date of signing the ICF and onwards. All AEs will be coded by system organ class (SOC) and preferred term (PT) using Medical Dictionary for Regulatory Activities (MedDRA) version 25.1.

Summaries will present non-treatment emergent AEs (AEs started before first day of treatment) and treatment-emergent AEs (TEAE; AEs started after first day of treatment) separately.

In an overview table, the number and percentage of participants who experienced a TEAE, non-TEAE, serious TEAE, treatment related TEAE, died due to an AE, or discontinued from study treatment due to a TEAE will be summarized by treatment.

The percentages of participants with TEAEs will be summarized by treatment using MedDRA preferred term nested within system organ class (SOC). Events will be ordered by decreasing frequency within SOC, and SOC with be ordered by decreasing frequency.

Similar summary will be presented for non-TEAE, serious TEAE, treatment related TEAE and TEAE related to worsening of migraine.

AEs with missing start date will be considered as a TEAE.

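### SAP 6.1 lists but does not analyse scale scores from an Early Termination visit, even when the visit falls inside a scheduled visit window; the effect is small and confined to secondary and exploratory scales

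*SAP*

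**What the plan says.** SAP 6.1 sets a general rule: "Measurements taken at Early Termination visit/withdrawal will be presented in listings but will not be included in summaries and analyses". The visible text gives no exception for a visit that falls on schedule.

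ET data exist by design. Protocol 7.2 says: "Participants who prematurely discontinue study participation must complete the early termination procedures as described in the SoA". Protocol 7.1 asks the same of anyone who permanently stops the intervention. In the schedule of activities (Protocol 1.2), ET shares one column with Week 12, and MSQ, MIDAS and PGI-C are all marked there. The Week 4, 8 and 12 visits are set at Days 29, 57 and 85, each ±3 days.

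On the analysis side, SAP 8.5.6 says: "The MSQ is a 14-item questionnaire that is completed at baseline, Week 4, Week 8, and Week 12". SAP 8.5.6 to 8.5.8 then test the change at each of the three post-baseline visits separately. MIDAS is tested at Week 12 (SAP 8.5.9), and PGI-C is measured at Week 12 (SAP 8.8). For both MSQ and MIDAS the SAP adds: "This analysis will use observed data only". SAP 8.8 states no imputation for PGI-C.

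**The concern.** Under these rules the visit label decides whether a score is used. An MSQ completed on Day 57 enters the Week 8 analysis if the visit is recorded as Week 8, and goes to a listing if it is recorded as ET. The instrument and the day are the same. Days 82–84 are the least clear case: they lie in the Week 12 window, and the schedule puts Week 12 and ET in a single column.

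The scores removed come only from people who stop early. Because the analyses use observed data, no imputation makes up for them. If stopping is related to outcome and differs between arms, leaving out valid on-schedule scores can bias the comparison of arms on these scales.

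**Working it through.** **The plan's own figures.** SAP 4.2 assumes a difference of 1.6, SD 5.8, 85% power and two-sided alpha 5%. The two-sample t-test gives 236.93, so 237 per arm and 474 in total. With 15% drop-out, 474 / 0.85 = 557.6, so 558. Both stated figures reproduce, and this point does not affect them.

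**Inputs**
- Randomised: 558; drop-out: 15% (SAP 4.2).
- Windows in protocol day numbers: 26–32, 54–60 and 82–88 (Protocol 1.2). The app stops after Day 84, so only 82–84 of the last window can be an early stop.
- Assumptions not in the documents: every drop-out attends an ET visit on the day of stopping; stopping days are uniform over Days 1–84; no scheduled score for that window has already been taken.

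**Number of ET visits:** 558 × 0.15 = 83.7, about 84.

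**In-window days:** 7 + 7 + 3 = 17 of 84, or 20.2%.

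**Scores affected**

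| Analysis | In-window days | 83.7 × days / 84 |
|---|---|---|
| MSQ Week 4 | 7 | 7.0 |
| MSQ Week 8 | 7 | 7.0 |
| MSQ Week 12 | 3 | 3.0 |
| MSQ, all three | 17 | 16.9 |
| MIDAS or PGI-C, Week 12 | 3 | 3.0 |

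The MSQ total of about 17 is 17 / 558 = 3.0% of those randomised. It is spread over three separate analyses, so no single one loses more than about 7, or 7 / 558 = 1.3%.

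**Sensitivity to drop-out (MSQ total):** 5% gives 27.9 × 17 / 84 = 5.6; 10% gives 55.8 × 17 / 84 = 11.3; 20% gives 111.6 × 17 / 84 = 22.6.

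**Sensitivity to Days 82–84:** Protocol 4.4 counts those who complete the Day 84 (Week 12) assessments as completers, so many visits on these days may be recorded as Week 12. Without them, 83.7 × 14 / 84 = 13.95, about 14 for MSQ and none for MIDAS or PGI-C.

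**Possible bias.** Leaving out a fraction f of an arm's scores, whose mean differs by D from the rest, moves that arm's mean by f × D. If all 7 scores at one visit fell in one arm of 279, f would be 7 / 279 = 2.5% of those randomised to it. The documents give no value for D.

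**Day numbering.** SAP 6.1 takes study day as date minus baseline date, so baseline is Day 0; the protocol calls it Day 1. Protocol Days 29, 57 and 85 are therefore SAP study days 28, 56 and 84. Any rule added to SAP 6.1 must use the SAP numbers or say which system applies.

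**The case against.** The strongest reply is that listing ET scores separately is a deliberate, pre-specified choice and that little depends on it. Much of this stands. SAP 8.6 makes secondary and exploratory p-values and intervals nominal, not for inference. The primary endpoint comes from the daily eDiary (SAP 6.3), so this rule by itself removes no primary data. A stop on Day 31 costs nothing if the Week 4 visit took place on Day 29, and participants lost to follow-up may never attend ET. A MIDAS score at a Day 57 ET visit would drop out of by-visit descriptive summaries only, because the test is at Week 12. Finally, most of SAP 6.3 and all of Appendix A are missing from the public text, so a visit-mapping rule may exist there.

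What does not fall is that SAP 6.1 states an exclusion, and nothing visible explains why the label should override the window.

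Two stronger readings are tempting, and the documents support neither.
- A reader might infer that adverse events elicited at the ET visit disappear from the safety tables. But SAP 6.1 speaks of measurements at a visit, whereas SAP 9 classifies events by onset relative to first treatment, without filtering by visit. Its overview table covers those who "discontinued from study treatment due to a TEAE will be summarized by treatment". Protocol 8.4.1 says: "All AEs and SAEs will be collected from the signing of the informed consent form (ICF) until the follow-up visit", and Protocol 9.4.8 summarises events recorded through the study. Concomitant medications are defined by end date (SAP 7.3), and discontinuation reasons come from the eCRF (Protocol 7.2) and are tabulated in disposition (SAP 7.1).
- A reader might also infer a contradiction with SAP 2.2, which says: "The treatment effect of interest is regardless of early discontinuation of treatment which complies with the treatment policy strategy". That estimand concerns migraine days, not visit scales, so at most the two approaches sit uneasily together.

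**Conclusion.** The point holds for the scales only. On the visible text, an on-schedule MSQ, MIDAS or PGI-C score labelled ET is listed and not analysed, and for MSQ and MIDAS it is explicitly not replaced. The loss is confined to early stoppers.

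The size is small: about 17 participants for MSQ and about 3 for MIDAS and PGI-C. These are ceilings given 15% drop-out, full ET attendance, uniform stopping and no scheduled score already taken. Relaxing attendance, or allowing for scores already taken, lowers them; stopping that clusters around scheduled visits could raise them. Without those assumptions the number could lie anywhere from none to all of the roughly 84 ET visits.

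The case for changing the sentence is that the exclusion is selective and cheap to remove, not that it threatens the trial's conclusion. Scales whose rows are blacked out in the public schedule cannot be assessed.

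**What to change.** Limit the SAP 6.1 sentence to effectiveness scales, and add:

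*An ET scale score falling within the protocol window of a scheduled visit (Week 4, 8 or 12 ± 3 days; SAP study days 28, 56 and 84, since baseline is Day 0) is analysed at that visit if no scheduled score exists. Other ET scale scores are listed only.*

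If SAP 6.3 or Appendix A already contains a mapping rule, a cross-reference from SAP 6.1 is enough. As an optional clarification, state that the sentence does not apply to safety data; SAP 9 already includes adverse events elicited at ET.

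The cost is a line of SAP text and one visit-mapping rule in programming. The downside is that a few analysed scores would come from the day of stopping. The sample size and the primary analysis do not change.
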